### Appendix D - Dose Adjustment Rules for Patients who have TI for $\geq 56$ Days (8 weeks) – Maintenance Phase

A modified dose adjustment algorithm will apply to patients who have attained TI  $\geq 56$  days. The down titration of the dose is allowed at any time.

Change in Hb from 4 weeks earlier (g/dL)	Hemoglobin (Hb) Values			
	Hb <10.5 g/dL	Hb 10.5 to 12.9 g/dL	Hb >13.0 g/dL	Hb $\geq 13.5$ g/dL
< -1.0 * (or had RBC transfusion within 4 weeks)	↑	↑	No change	Hold, then resume dosing when: Hb <12 g/dL, at a dose that is reduced by one-dose level  Patients are to return weekly to monitor Hb until dosing can be resumed
-1.0 to 1.0	↑	No change	↓	
> 1.0	No change**	↓	↓	

\* A change in Hb from 4 weeks earlier of < -1.0 g/dL means a Hb value that is lower by more than 1.0 g/dL compared to 4 weeks earlier, e.g., a Hb of 9.4 g/dL compared to 10.6 g/dL 4 weeks earlier

#### \*\*Dose Adjustment for Excessive Hematopoiesis During Maintenance Phase:

At any time during the Treatment Period of the maintenance phase if Hb increases by >2.0 g/dL within 4 weeks, the dose should be reduced by one dose level.

## Appendix E – Quality of Life Assessments

The following health-related quality of life (HRQoL) assessment tools will be utilized for this study:

1. Patient-Reported Outcomes Measurement Information System (PROMIS®), [Cella et al. 2007](#); [Cella et al., 2010](#))
2. European Quality of Life Five Dimensional Health Questionnaire (EQ-5D-5L), ([Rabin and de Charro, 2001](#))

The rationale for each of the PRO items and domains selected includes consideration of the applicable concepts to be evaluated and context of use for this study.

Specific symptoms that are most important to the MDS population are fatigue/tiredness. Currently, there are no existing perfect measures to capture these symptoms.

PROMIS provides clinicians and researchers access to reliable, valid, and flexible measures of health status that assess physical, mental, and social well-being from the patient perspective. PROMIS measures are standardized, allowing for assessment of many patient-reported outcome domains, including pain, fatigue, emotional distress, physical functioning and social role participation, based on common metrics that allow for comparisons across domains, across chronic diseases, and with the general population. Further, PROMIS tools allow for computer adaptive testing, efficiently achieving precise measurement of health status domains with few items. There are PROMIS measures for both adults and children. PROMIS was established in 2004 with funding from the National Institutes of Health (NIH) as one of the initiatives of the NIH Roadmap for Medical Research.

EQ-5D is a standardized instrument for measuring generic health status. The health status measured with EQ-5D is used for estimating preference weight for that health status, then by combining the weight with time, quality-adjusted life year (QALY) can be computed. QALYs gained is used as an outcome in cost-utility analysis which is a type of economic evaluation that compares the benefit and cost of health care programs or interventions. Many countries generated a value set (preference weights) of their own population and have used it for estimating QALY to make decisions in resource allocation. There are currently 171 language versions of EQ-5D questionnaire available. EQ-5D is one of the most commonly used generic health status measurement, and its good validity and reliability have been reported in various health conditions.

Importantly, PROMIS is a validated instrument for the MDS population ([Abel et al., 2014](#)), and so is EQ-5 ([Efficace, 2015](#)).

**Appendix F – ECOG Assessment Scale**

---

Grade	ECOG
0	Fully Active, able to carry on all pre-disease performance without restriction
1	Restricted in physically strenuous activity but ambulatory and able to carry out work of light or sedentary nature, e.g., light house work, office work
2	Ambulatory and capable of all self-care but unable to carry out any work activities. Up and about more than 50% of waking hours
3	Capable of only limited self-care, confined to bed or chair more than 50% of waking hours
4	Completely disabled. Cannot carry on any self-care. Totally confined to bed or chair
5	Dead

---

**Appendix G – International Prognostic Scoring System – Revised (IPSS-R)*****International Prognostic Scoring System***

Prognostic variable	0	0.5	1	1.5	2	3	4
Cytogenetics	Very Good		Good		Intermediate	Poor	Very Poor
BM* Blast %	≤2		>2-<5%		5-10%	>10%	
Hemoglobin	≥10		8-<10	<8			
Platelets	≥100	50-<100	<50				
ANC**	≥0.8	<0.8					

\* bone marrow

\*\* absolute neutrophil (white blood cell) count

***IPSS-R Risk Groups***

Risk Group	Risk Score
Very Low	≤1.5
Low	> 1.5-3
Intermediate	> 3-4.5
High	> 4.5-6
Very High	> 6

## Appendix H – Liver Function Monitoring

The guidelines described in this section are intended to enable early detection and action following abnormal liver function test (LFT) results. Any patient enrolled in a clinical study with active drug therapy and reveals an increase of serum aminotransferases (AT) to  $> 3 \times$  upper limit of normal (ULN), or bilirubin  $> 2 \times$  ULN, should undergo detailed testing (including at least alanine aminotransferase [ALT], aspartate aminotransferase [AST], alkaline phosphatase [ALP], and total bilirubin [TBL]) for further evaluation and follow-up. Alerts will be generated by the central lab to inform the investigator, study monitor and study team. Testing should be repeated within 48-72 hours of notification. Patients should be asked if they have any symptoms suggestive of hepatobiliary dysfunction.

### Definition of Liver Abnormalities

Confirmed abnormalities should be characterized as follows:

	ALT or AST		Total Bilirubin
Moderate	$> 3 \times$ ULN	Or	$> 2 \times$ ULN
Severe	$> 3 \times$ ULN	And	$> 2 \times$ ULN

Abbreviations: ALT = alanine aminotransferase; AST = aspartate aminotransferase; ULN = upper limit of normal.

Hy's Law: Drug-induced jaundice caused by hepatocellular injury, without a significant obstructive component, has a high rate of bad outcomes, from 10% to 50% mortality (or transplant). The two "requirements" for Hy's Law are: 1) Evidence that a drug can cause hepatocellular-type injury, generally shown by an increase in transaminase elevations higher than 3 times the upper limit of normal (" $2 \times$  ULN elevations are too common in treated and untreated Patients to be discriminating"). 2) Cases of increased bilirubin (at least  $2 \times$  ULN) with concurrent transaminase elevations at least  $3 \times$  ULN and no evidence of intra- or extrahepatic bilirubin obstruction (elevated alkaline phosphatase) or Gilbert's syndrome: Temple, R (2006) Hy's law: predicting serious hepatotoxicity. *Pharmacoepidemiol Drug Saf* **15**: (4):241-243

In addition, the patient should be considered to have severe hepatic abnormalities for any of the following:

- ALT or AST  $> 8 \times$  ULN
- ALT or AST  $> 5 \times$  ULN for more than 2 weeks
- ALT or AST  $> 3 \times$  ULN and international normalized ratio (INR)  $> 1.5$  (if INR testing is applicable/evaluated).
- ALT or AST  $> 3 \times$  ULN with the appearance of fatigue, nausea, vomiting, right upper quadrant pain or tenderness, fever, rash and/or eosinophilia ( $> 5\%$ ).

The investigator may determine that abnormal liver function results, other than as described above, may qualify as moderate or severe abnormalities and require additional monitoring and follow-up.

## Follow-up Procedures

Patients with confirmed abnormal liver function results should be closely monitored and followed as described below. If close monitoring for LFTs in a patient is not possible, study drug should be discontinued.

Repeat LFTs 2-3 times weekly, then weekly or less until abnormalities stabilize or return to within normal limits. LFTs should include ALT, AST, TBL and ALP

In addition, evaluate the patient for potential causes, which may include the following:

- Detailed history of symptoms and prior or concurrent diseases
- Concomitant drug use, including nonprescription medications, herbal and dietary supplements, alcohol or recreational drug use, or special diets
- Exposure to environmental chemical agents
- Rule out acute viral hepatitis Types A,B,C,D,E; autoimmune or alcoholic hepatitis; nonalcoholic steatohepatitis; hypoxic/ischemic hepatopathy; biliary tract disease
- Obtain additional tests as appropriate: e.g., INR, gamma glutamyltransferase (GGT) or direct bilirubin; ultrasound or other imaging to assess biliary tract disease
- Consider gastroenterology or hepatology consultations

In general, in the absence of an explanation for increased LFTs, such as viral hepatitis, preexisting or acute liver disease or exposure to other agents associated with liver injury, the study drug should be discontinued.

Discontinuation of treatment should be considered if:

- ALT or AST  $> 8 \times$  ULN
- ALT or AST  $> 5 \times$  ULN for more than 2 weeks
- ALT or AST  $> 3 \times$  ULN and TBL  $> 2 \times$  ULN or INR  $> 1.5$  (If INR testing is applicable/evaluated)
- ALT or AST  $> 3 \times$  ULN with the appearance of fatigue, nausea, vomiting, right upper quadrant pain or tenderness, fever, rash and/or eosinophilia ( $> 5\%$ )

Once LFTs return to normal, and depending on whether there is an explanation for the LFT elevations, study drug dosing may resume, after discussion with the Medical Monitor

See also: FDA Guidance for Industry, titled: “Drug-Induced Liver Injury: Premarketing Clinical Evaluations”, issued July 2009

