### 4.3 Treatment Discontinuation

Patients who discontinue study medication early (for any reason) will remain in the study through the 52 week study period. Patients will have a 4 week follow-up visit after stopping study medication and then be followed up at a reduced visit schedule of every 8 weeks until the end of the study.

Patients will be discontinued from treatment for the following reasons (below and [Appendix H](#) and [Appendix O](#)):

- a. Disease progression: Diagnosis of AML during the study
- b. Liver Function: Discontinuation of treatment will occur if:
  - ALT or AST  $>8 \times$  ULN
  - ALT or AST  $>5 \times$  ULN for more than 2 weeks
  - ALT or AST  $>3 \times$  ULN and TBL  $>2 \times$  ULN or international normalized ration (INR)  $>1.5$  (If INR testing is applicable/evaluated)
  - ALT or AST  $>3 \times$  ULN with the appearance of fatigue, nausea, vomiting, right upper quadrant pain or tenderness, fever, rash and/or eosinophilia ( $>5\%$ )

A patient who decides to discontinue treatment with study medication will always be asked about the reason(s) for discontinuation and the presence of AEs (if any). These data will be ascertained and documented by the investigator and recorded in the electronic case report forms (eCRF) as appropriate. The patient should return all study medications.

Reasons for permanent discontinuation of treatment with study medication:

- Patient's decision (subject no longer wants to continue study medication (i.e., withdrawal of consent)
- Investigator's decision that it is in the best interest of the patient to be withdrawn from the study
- AEs (including SAEs)
- Significant noncompliance with study procedures, as determined by Investigator or Sponsor
- Lack of efficacy
- Treatment with ESAs
- Patient is lost to follow-up
- Site terminated by the Sponsor
- Pregnancy
- Death

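### Protocol Section 4.3 and Appendix O require stopping for four liver criteria, while Appendix H makes the same stop discretionary and then allows dosing to resume

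*Protocol*

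**What the plan says.** **Protocol Section 4.3** opens with "Patients will be discontinued from treatment for the following reasons (below and" and then names Appendix H and Appendix O. Its liver item reads "Liver Function: Discontinuation of treatment will occur if" and lists four criteria. **Appendix O**, the individual stopping criteria, has the same liver lead-in and the same list.

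**Appendix H**, under Follow-up Procedures, lists the four criteria under "Discontinuation of treatment should be considered if". Three other sentences there bear on the action to take:

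- On unexplained rises, one sentence sets a condition that begins "In general, in the absence of an explanation for increased LFTs, such as viral hepatitis, preexisting or acute liver disease"; where nothing of that kind accounts for the rise, its advice is to stop.
- On monitoring: "If close monitoring for LFTs in a patient is not possible, study drug should be discontinued".
- After liver tests return to normal, and depending on whether the rise has an explanation: "study drug dosing may resume, after discussion with the Medical Monitor".

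Appendix H describes its own status this way: "The guidelines described in this section are intended to enable early detection and action".

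**Where sites are sent.** Section 3.5 refers liver abnormalities to Appendix H. Footnote 8 to the Appendix A schedule refers to Appendix H and Appendix O together.

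**SAP Section 7, Table 2, item 4** counts as a major deviation a patient who reaches the criteria for stopping but stays on drug. Major deviations are the basis for removing patients from the per-protocol set.

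**The concern.** An individual stopping rule should give one answer for one laboratory result. Here the same result leads to a compulsory stop in two places and to a decision left open in a third. Section 4.3 cites that third text as part of its own rule. Appendix H itself classes these findings as severe hepatic abnormalities, so the ambiguity concerns patient safety.

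Two things are at stake. With about 80 centres planned, patients with the same result could be handled differently from site to site. And a site that followed Appendix H in good faith could find its patient recorded as a major deviator, because the deviation rule in the SAP turns on whether the criteria required stopping.

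**Working it through.** No figure in the plan depends on this rule, so the check is a comparison of the current texts.

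**Step 1. Compare the three lists.**

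| Criterion | Section 4.3 | Appendix O | Appendix H |
|---|---|---|---|
| ALT or AST >8 × ULN | stop | stop | consider |
| ALT or AST >5 × ULN for over 2 weeks | stop | stop | consider |
| ALT or AST >3 × ULN with TBL >2 × ULN or INR >1.5 | stop | stop | consider |
| ALT or AST >3 × ULN with the listed symptoms or signs | stop | stop | consider |

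All four criteria match in content and threshold across the three texts. Only the lead-in differs: mandatory in two, discretionary in one.

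**Step 2. Find the patients for whom it matters.** Take a patient who meets one of the four criteria.

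| Situation | Section 4.3 and Appendix O | Appendix H read as a whole | Conflict |
|---|---|---|---|
| Close monitoring not possible | stop | should stop | little |
| Rise unexplained, monitoring possible | stop | should in general stop | little |
| Rise explained, monitoring possible | stop | consider stopping | yes |

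The conflict is concentrated in the last row, for example viral hepatitis or exposure to another agent associated with liver injury.

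**Step 3. Look at resumption.** Section 4.3 and Appendix O do not mention restarting after a liver stop; Appendix H allows it. Section 4.3 also gives a separate list of reasons for permanent discontinuation, and Section 3.3.2 limits a dose hold to one instance of at most 2 weeks. Neither says whether a stop under the four criteria is permanent. Changing the Appendix H lead-in alone would leave that open.

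**Step 4. Trace the effect on the analysis.**

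- *Per-protocol set.* A patient in the last row who is kept on drug complies with Appendix H but falls within SAP Table 2 item 4 if Section 4.3 governs. Exclusion would alter the per-protocol sensitivity analyses.
- *Full analysis set.* Under SAP Section 5.3.1, membership needs randomization, one dose and one on-treatment Hb value, so it does not depend on the liver rule. The only route into the primary result is that transfusion independence is assessed up to end of treatment, so stopping or continuing changes that one patient's observation period.

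**Step 5. Size.** The documents give no rate for meeting a criterion or for having an alternative explanation, so no number of patients can be derived.

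**The case against.** The best defence is that the documents largely show which text governs. Section 4.3 and Appendix O are headed as discontinuation and stopping rules; Appendix H is headed as monitoring and calls its content guidelines. A site that stops the drug satisfies both wordings, and nothing tells a site to continue. Section 4.3 and schedule footnote 8 point to both appendices, so a site is unlikely to see only the discretionary version. Central-laboratory alerts, retesting within 48-72 hours and liver tests 2-3 times weekly add protection.

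Most of this stands. It lowers the chance of a missed stop and supports correcting Appendix H, not the other two texts. It does not remove the conflict: no sentence states precedence, Section 4.3 brings Appendix H into its own rule, and alerts and retesting detect the event without saying what must be done.

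A reader might also infer from the Amendment 02 change log that the mandatory wording was agreed and Appendix H was overlooked. The log does not show that. It describes superseded text and says the other two places were brought into line with Appendix H, whose supplied text is discretionary. The direction of the fix rests on Section 4.3 and Appendix O alone.

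**Conclusion.** The inconsistency is real in the Amendment 02 text. It is one lead-in phrase in one of three places, plus a resumption sentence whose scope is unstated. Severity is low to moderate: the rule protects patients, but the divergence is mainly for those who meet a criterion, have an alternative explanation and can be closely monitored.

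Two stronger readings are tempting and not supported. One is that Appendix H leaves sites free to keep dosing through serious liver findings in general; it advises stopping for unexplained rises and where monitoring is not possible. The other is that the trial's main result is at risk. The primary analysis on the full analysis set is essentially unaffected; the analytic consequence is confined to possible per-protocol exclusions.

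The conclusion assumes that the supplied text is still in force. The SAP is written against Amendment 03 (30 January 2020), which was not supplied and may already have corrected this.

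**What to change.** First check Appendix H in Amendment 03. If it is unchanged, make one edit with two parts:

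1. Replace the discretionary lead-in to the four criteria with the mandatory lead-in used in Section 4.3 and Appendix O.
2. State whether the resumption sentence applies to a patient who met one of the four criteria. One option is to limit it to patients whose drug was held for liver test rises that met none of them.

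The second part is needed, because a compulsory stop followed by an unqualified permission to restart could still be applied differently between sites. The cost is one phrase and one sentence in Appendix H. Design, sample size and SAP stay as they are, and SAP Table 2 item 4 then has a single rule to refer to.

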**Appendix I – Erythropoiesis-Stimulating Agents (ESAs)**

Prohibited ESAs include (but are not limited to) the following:

- darbepoetin
- Mircera (methoxy polyethylene glycol epoetin beta)
- epoetin alfa
- epoetin beta
- epoetin delta
- epoetin theta
- epoetin omega
- hematide

**Appendix J – Schedule of PK Assessments**

Timing and Number of PK Samples; note that Vital Signs will be taken prior to each blood draw

	0-2 hrs pre-dose ^	1-3 hrs	2-3 hrs	3-5 hrs	4-6 hrs	8-10 hrs
Day 1 (Week 1)		1		1		
Week 5					1	
Week 21						1
Week 25	1		1			

^Time points are post-dose unless specified otherwise

**Appendix K – Laboratory Tests**

CBC:
 
 
Basophils
 
Eosinophils
 
Erythrocyte count (RBC)
 
HCT
 
Hb
 
Leukocyte count (WBC)
 
Lymphocytes
 
Mean corpuscular volume
 
Mean corpuscular Hb
 
Mean corpuscular Hb concentration
 
Monocytes
 
Neutrophils
 
Neutrophils, immature (banded)
 
Platelets
 
 
Iron Biomarkers:
 
 
Ferritin
 
Iron
 
TIBC
 
UIBC
 
TSAT
 
 
Additional Hematology Analytes:
 
 
Reticulocyte count
 
CHr
 
	
Serum Chemistry:
 
 
Albumin
 
Bicarbonate
 
BUN
 
Calcium
 
Chloride
 
Creatinine
 
Glucose
 
Lactate dehydrogenase
 
Magnesium
 
Phosphorus
 
Potassium
 
Na
 
 
LFTs:
 
 
ALP
 
ALT
 
AST
 
TBili
 
 
HIV and Viral Hepatitis Panel:
 
 
Anti-HCV Ab tests
 
HBsAg
 
HIV
 

Special Laboratory Tests:
 
 
Hepcidin
 
Serum erythropoietin level
 
Serum Lipid Panel (non-fasting) including total cholesterol, LDL and TG
 
Point-of-care Urine Pregnancy Test
 
	

Abbreviations: ALP = alkaline phosphatase; ALT = alanine aminotransferase; AST = aspartate aminotransferase; BUN = blood urea nitrogen; CBC = complete blood count; CHr = reticulocyte hemoglobin content; Hb = hemoglobin; HBsAg = hepatitis B surface antigen; HCT = hematocrit; HCV = hepatitis C virus; HIV = human immunodeficiency virus; LDH = lactate dehydrogenase; LDL = low density lipoprotein; PT = prothrombin time; PTT = partial thromboplastin time; RBC = red blood cell; TBili = total bilirubin; TG = triglycerides; TIBC = total iron binding capacity; UIBC=unsaturated iron binding capacity; TSAT = transferrin saturation; WBC = white blood cell.

## Appendix L – Calculation of Creatinine Clearance/eGFR per Cockcroft-Gault

The Cockcroft-Gault (CG) formula (Cockcroft and Gault, 1976; Gault, 1992) estimates GFR in ml/min and employs serum creatinine measurements and a patient's weight to predict the creatinine clearance as follows:

$$eC_{Cr} = \frac{(140 - \text{Age}) \times \text{Mass (in kilograms)} \times [0.85 \text{ if Female}]}{72 \times \text{Serum Creatinine (in mg/dL)}}$$

When serum creatinine is measured in  $\mu\text{mol/L}$ , the following formula applies:

$$eC_{Cr} = \frac{(140 - \text{Age}) \times \text{Mass (in kilograms)} \times \text{Constant}}{\text{Serum Creatinine (in } \mu\text{mol/L)}}$$

Where Constant is 1.23 for men and 1.04 for women.

A web-based Cockcroft-Gault calculator can be accessed at <http://nephron.com/cgi-bin/CGSI.cgi>.

## **Appendix M – New York Heart Association Classification (NYHA) of Congestive Heart Failure**

The list below describes the most commonly used classification system, the NYHA Functional Classification. It places patients in one of four categories based on how much they are limited during physical activity.

### **Class Patient Symptoms**

- I Cardiac disease, but no symptoms and no limitation in ordinary physical activity, e.g., no shortness of breath when walking, climbing stairs etc.
- II Mild symptoms (mild shortness of breath and/or angina) and slight limitation during ordinary activity.
- III Marked limitation in activity due to symptoms, even during less-than-ordinary activity, e.g., walking short distances (20–100 m). Comfortable only at rest.
- IV Severe limitations. Experiences symptoms even while at rest. Mostly bedbound patients.

## **Appendix N – Blood Pressure and Heart Rate Monitoring**

### ***Blood Pressure***

Blood pressure (BP) measurement should be done with the patient comfortably seated in a chair, with the legs uncrossed, and the back and arm supported, such that the middle of the cuff on the upper arm is at the level of the right atrium (the midpoint of the sternum). The patient should be instructed to relax as much as possible and to not talk during the measurement procedure. Preferably measurement will be done with an electronic automated device. The same device should preferably be used for the patient during the course of the study, timing as indicated in the Schedule of Assessments. Also the same arm should be used consistently for readings throughout the study.

